#### **General Goal**

The goal of this study is to understand the neural basis of human consciousness and its modulation by anesthetic agents supported by Departmental Research Funds. The fundamental question is how the state and contents of consciousness are intertwined in the brain. As previously defined [1], state distinguishes the conditions or levels of being aware of anything at all from that being completely oblivious such as in general anesthesia or coma. Contents of consciousness refers to what one is aware of at a particular moment vs. what is outside of immediate awareness. Our central hypothesis is that state and contents are linked by a cooperation between the anterior forebrain mesocircuit and macroscale cortical networks, and that this cooperation is controlled by a few key brain areas (Fig. 1). To investigate, we will combine pharmacologic, psychologic and noninvasive brain stimulation approaches. We will alter the state of consciousness by propofol in healthy volunteers, and assess the contents of consciousness by applying a near-threshold perceptual task with Signal Detection Theory (SDT) metrics. Task-related brain activity will be assessed by simultaneous fMRI. We will also apply transcranial low-intensity focused ultrasound pulsation (LIFUP) to stimulate specific brain regions and assess their causal involvement in the control of conscious state and contents. From a basic science perspective, this work will help understand the neural basis of consciousness, which is one of the most fundamental unsolved problems of neuroscience. From a clinical perspective, the work will facilitate better understanding of the neural mechanism of the anesthetics' sedative-hypnotic effects, which is a prerequisite for future enhancements of clinical anesthesiology.

**Fig. 1.** Schematic illustration of the central hypothesis. The state and contents of consciousness are linked by a cooperation between the anterior forebrain mesocircuit and the macroscale cortical networks, controlled by a few key brain areas. The central thalamus (CT) controls the state of consciousness. The anterior insula cortex (AIC) gates conscious contents and regulates brain network switches between dorsal attention (associated with external awareness) and default mode (associated with internal awareness)

networks. The dorsolateral prefrontal cortex (DLPFC) within the lateral frontoparietal network has a flexible cooperation with the dorsal attention and default mode networks, and it initiates brain-wide global broadcasting of contents that leads to reportable conscious experience known as access consciousness. Macroscale brain networks unfold along a hierarchical cortical organization from unimodal to transmodal regions. The CT, AIC and DLPFC are target areas with LIFUP. Abbreviations: medial prefrontal cortex (MPFC), posterior cingulate cortex (PCC), posterior parietal cortex (PPC), frontal eye field (FEF), superior parietal lobe (SPL), anterior cingulate cortex (ACC).

# **Rationale and Hypothesis**

Investigations into the state and contents of consciousness have traditionally progressed independently. However, we previously proposed that the state and contents of consciousness are fundamentally linked, and they can be neither studied nor understood in isolation from each other [2]. Thus, a gap of knowledge exists, mainly due to the lack of systematic investigations into both aspects of consciousness with the same experimental setup. The research proposed here is designed to overcome this gap by discovering the neural linkages between state and contents of consciousness. Our general hypothesis is that the relationship between state and contents of consciousness rests on the functional interaction of brain systems between meso- and macroscales. At mesoscale, the "anterior forebrain mesocircuit" hypothesis [3-5] encapsulates the role of central thalamic (CT) neurons and their frontostriatal connections in determining the state of consciousness. The mesocircuit also incorporates acceding projections from brainstem arousal nuclei and cooperates with the frontoparietal cortical network to generate conscious experience [5]. At macroscale, the contents of consciousness are thought to be determined through a hierarchical cortical organization along a cortical gradient from unimodal to transmodal areas [6]. Prior studies suggest the involvement of specific brain regions; particularly that of the AIC which gates conscious access of sensory information [7] by controlling the balance of activity between the default-mode and dorsal attention networks that correspond to internal and external awareness, respectively [8,9]. In addition, the DLPFC is thought to initiate brain-wide global broadcasting of contents to generate reportable conscious experience known as access consciousness [10-12].

In this study, we aim to determine how conscious contents are degraded during anesthetic modification of the conscious state, and to disentangle the causal roles of specific brain areas in state-content interaction through a perturbational approach. We hypothesize that suppressing the state of consciousness will diminish the quality of conscious contents and that this will be associated with functional alterations in three key brain areas: CT, AIC and DLPFC. We also hypothesize that stimulating the three areas will lead to differential perceptual outcomes (e.g., a change in subjective perceptual criterion alone, detection sensitivity alone, or both).

To test the hypotheses, we will (1) administer propofol to reduce the state of consciousness (moderate sedation), (2) perform near-threshold perceptual task to assess the contents of consciousness, (3) apply transcranial low-intensity focused ultrasound pulsation (LIFUP) to noninvasively stimulate the CT, AIC and DLPFC, and (4) perform functional magnetic resonance imaging (fMRI) to measure the related brain process during baseline, sedation, and sedation+LIFUP. We will measure the quality of conscious contents by two orthogonal quantities, criterion (c) and sensitivity (d') derived from the Signal Detection Theory. Here c captures the tendency of a subject to report subjective recognition of a target stimulus regardless of whether the target is present or absent, whereas d' captures the ability of a subject to distinguish between target present and absent trials.

We anticipate that suppressing the conscious state will decrease both c and d', indicating more conservative responses and reduced stimulus differentiation, while c and d' are differentially affected by the activity of DLPFC and AIC. Furthermore, neither c nor d' alone but their product will be associated with the activity of the CT, thus implying a putative mechanism for state-content

relationship by the functional interaction of brain areas CT for controlling state, and AIC and DLPFC for gating and broadcasting, respectively, the conscious contents. We also anticipate that stimulating the DLPFC and AIC will differentially change c and d'. Stimulating the CT will positively shift c and substantially increase d', thereby restoring perceptual performance to the awake baseline level. This will be associated with an increase of task-related activity in the DLPFC and AIC. If so, this would disentangle the causal roles of CT, AIC and DLPFC on perceptual outcomes.

# **Number of Subjects, Recruitment and Informed Consent**

Statistical power analysis (see below) requires a group of 25 subjects. We plan to enroll 100 evaluable subjects randomly assign into four groups; we intend to enroll 150 subjects to account for unevaluable participants. See experimental design details below. Healthy participants will be recruited by listing on UMClinicalStudies.org and by postings at area colleges and community groups in Ann Arbor. Interested volunteers will call the phone number of a designated recruiter for an initial phone screening. The initial phone screening will consist of questionnaires related to medical history, demographic information, handedness, inclusion and exclusion criteria and procedure standard MRI screening questionnaire. If interested, the participant will complete the questionnaires, which will be reviewed by the study team. The health status will be confirmed by the attending anesthesiologist before the study on site. Once eligibility is confirmed by the study team, the one-time research study session will be scheduled. Participants will screened for COVID-19 prior to entry into the hospital per hospital guidelines. A standard face mask will be provided upon hospital entry if participants do not have one.

All participants will give written informed consent according to institutional guidelines prior to any testing. The Principal Investigators or their designee will obtain consent using a written consent form approved by the Institutional Review Boards of the University of Michigan Medical School (IRBMED). It will contain detailed information regarding the purpose, risks and benefits of participating. Copies of the signed consent form will be given to the subjects; the original consent will remain with the study team. Subjects will be compensated for their involvement.

#### **Inclusion and Exclusion Criteria**

Volunteers are screened using a medical history and demographics questionnaire.

*Inclusion criteria*. The subject population will consist of healthy study subjects with ASA-1 status. The participants' health status will be assessed by the attending anesthesiologist prior to inclusion in the study. The participants will be right-handed adults between the ages of 18 and 40 with a body mass index (BMI) less than 30. All subjects will be English speakers.

Exclusion criteria. Participants will be excluded if they have any medical contraindication to MRI scanning; are unable to undergo MRI scanning because of possible pregnancy or currently breastfeeding, BMI>30, metallic substances in the body, claustrophobia, anxiety, or cardiopulmonary disease; or have an intracranial structural abnormality on T1-weighted MRI scans. Potential subjects will be excluded if they have a history of allergy to propofol, eggs or egg products, soybean or soybean products, neurological, cardiovascular, or pulmonary illness; significant head injury with loss of consciousness; learning disability or other developmental disorder; sleep apnea or any severe snoring history; gastroesophageal reflux disease (GERD) or heartburn; pancreatitis or a history of pancreatitis, or sensory/motor loss sufficient to interfere with performance of the study. Participants with tattoos in the head or neck region will be excluded from study; other tattoos are subject to determination by investigators based on their assessment regarding participant safety. To eliminate aspiration risk subjects will also be excluded if they have had recent food or liquid intake (within 8 hours). Subjects will be excluded if they have a history of drug use, have a positive drug screen, are unwilling to abstain from alcohol for 24 hours prior to dosing, or have a current history of nicotine use. Women will be required to take a pregnancy

test prior to participation to ensure a negative result. The pre-scan drug screen and pregnancy test will be paid for by the study.

Participants will be compensated \$200 for completing the one-time fMRI scanning visit. Participants who have shaved or no hair, or those willing to shave the left side of their temple will be compensated an additional \$75.

#### **Methods and Procedures**

# **Imaging**

Noninvasive functional magnetic resonance imaging will be performed in the Philips 3T (MR2) Research MRI (standard 32-channel transmit/receive head coil) at the University of Michigan Health System, University Hospital, Department of Radiology.

- 1) SPGR high-resolution images. T1 weighted spoiled gradient recalled echo (SPGR) images will be acquired for high spatial resolution of anatomical images with parameters: 170 sagittal slices, 1.0mm thickness (no gap), TR=8.1s, TE=3.7ms, flip angle=8°, FOV=24cm, image matrix 256×256.
- **2) Functional MRI images.** A gradient-echo EPI pulse sequence will be employed to acquire functional images over the whole brain with parameters: 28 slices, TR/TE=800/25ms (multiband fMRI acquisition), slice thickness=4mm, in-plane resolution=3.4×3.4mm; MB factor=4; field of view (FOV)=220mm, flip angle=76°, image matrix: 64×64. The imaging protocols and data acquisition will be completed within 2.5 hours scanning session for each subject.

#### Anesthesia

Anesthetic agents. In both experiments, propofol will be applied because it has been the most widely-used agent in human fMRI studies of anesthetic effects in brain activity [13–16] and we have considerable experience in this field [7,17–21]. The advantage of propofol is that it exerts minimal effects on cerebral and systemic hemodynamics [22,23] and therefore does not confound the fMRI results. Propofol suppresses neuronal activity mainly through an enhancement of GABA-A receptor-mediated inhibition thus modulating widespread targets across the brain.

Anesthetic administration and monitoring. Both experiments will be performed by the attending anesthesiologists. Sedation will be achieved by target-controlled IV infusion of propofol. The IV line will be placed after application of a local anesthetic. Nasal cannula will be used for supplemental O2 and CO2 sampling. Spontaneous respiration, end-tidal CO2, heart rate, and electrocardiogram will be continuously monitored during the experiment. Noninvasive arterial pressure will be measured with magnetic resonance (MR)-compatible automatic monitor. Post anesthesia care will consist of checking vital signs for 1 hour by the nursing staff. A wheelchair will be provided to assist the participant if needed. All anesthesia equipment, supplies, and drugs will be provided by anesthesiologists from the University of Michigan Health System.

#### **LIFUP Method**

We will utilize the BrainSonix BXPulsar 1002 LIFUP System (BrainSonix Inc. http://www.brainsonix.com/). FDA has determined that our proposed clinical investigation is a nonsignificant risk (NSR) device study because it does not meet the definition of a significant risk (SR) device under 21 CFR 812.3(m) of the investigational device exemptions (IDE) regulation (21 CFR 812). An IDE application is not required to be submitted to, or approved by, FDA for a NSR study. This device contains a single-element, air-backed, spherical section ultrasound transducer with 61 mm diameter and 80 mm focal depth. The transducer is mounted in a plastic housing filled

with deionized, de-gassed water and sealed with a thin polyethylene membrane permeable to ultrasound. The transducer will be coupled to the scalp of the participant using a 3D-printed transducer holder that allows for sonication to occur in conjunction with ultrasonic standoff pads and ultrasound gel. The LIFUP system operates at a fundamental frequency of 650 kHz. Following the previous work [24,25], we plan to administer a pulse repetition frequency of 100 Hz and pulse width of 0.5 ms. A total of 30 sonications will be administered, with a derated spatial-peak temporal-average intensity (Ispta) of 720 mW/cm², each lasting 30 s, separated by 30 s pause intervals. Sonication will be administered in a 3 Tesla Philips scanner at University of Michigan Hospital. Using a rapid structural MRI sequence, the perpendicular will be adjusted along the apex of the transducer's concavity directly targeting a region of interest. We will utilize a neuronavigation system (Brainsight Navigation system, Brainbox Ltd, https://brainboxneuro.com/products/brainsight-tms-navigation) to ensure precise targeting and positioning of the transducer. At the target location, the estimated peak pressure will be 0.71 MPa, and the ultrasound beam width will be 5 mm. The estimated targeting accuracy (uncertainty) at the desired location is ±2.5 mm.

## **Experimental Design**

Three 30-min sessions will be conducted including wakeful baseline, moderate sedation, and the application of LIFUP under moderate sedation (sedation+LIFUP) with an effect-site concentrations of 1.5 µg/ml (Fig. 2). Moderate sedation will be achieved by IV infusion of propofol to achieve effect-site concentrations of 1.5 µg/ml. Infusion rate will be manually controlled. An initial bolus dose and subsequent infusion rate for each participant will be pre-determined based on a pharmacokinetic model [26] developed for target-controlled propofol infusion and implemented in software (STANPUMP [27]). A 5-min equilibration period between baseline and moderate sedation will be included. After sedation+LIFUP session, the infusion will be terminated allowing for spontaneous recovery of consciousness. A random group assignment will be applied in four groups of participants receiving LIFUP with sham control, or in the DLPFC, AIC, or CT, respectively.

[figure not shown]
[figure not shown]

Fig. 2. Concept, design and anticipated outcomes. In the hypothetical brain process (top left) visual

information propagates through ventral (V1/V2-->VOTC) and dorsal (V1/V2-->MTG-->PPC) pathways. The AIC receives inputs from the VOTC and prioritizes the inputs before sending them to the DLPFC for global broadcasting. The activities of DLPFC and AIC are hypothetically associated with two orthogonal SDT quantities, criterion (c) and sensitivity (d'). Given the wiring of the mesocircuit and thalamocortical loops (e.g., DLPFC-CT, and AIC-CT), the CT is hypothetically associated with the product of c and d'. Experimental design (bottom left) includes three fMRI sessions: wakeful baseline, moderate sedation, and LIFUP under moderate sedation. Participants will be assigned at random to four groups: those receiving LIFUP to DLPFC, AIC, CT or sham control. Anticipated effects are illustrated (right). Abbreviations: early visual cortex (V1/V2), ventral occipitotemporal cortex (VOTC), middle temporal gyrus (MTG), posterior parietal cortex (PCC).

Visual task. Participants will be asked to lay in the scanner, pay attention on the screen, and complete an image recognition task. All stimuli will be programmed using E-Prime (Psychology Software Tools, Pittsburgh, PA) and delivered via a visual presentation system designed for an MRI environment. Stimuli will be presented at the threshold of subjective recognition. An adaptive thresholding procedure will be conducted whereby image contrast will be titrated to reach a 50% subjective recognition rate for each subject. Stimuli will include two common visual object categories: faces and houses. Participants' task is to report the category ("F" or "H") of an image presented and their recognition experience ("Yes" or "No") (Fig. 3). Specifically, they will be instructed to report the object category regardless of their recognition experience and, in cases of unrecognized images, to make a genuine guess (two-alternative choice discrimination). Then, they will be instructed to report whether they see an object, such that even if the object appears unclear or noisy, they should respond "yes", but if they see nothing or only low-level features, such as cloud-like abstract patterns, they should respond "no".

**Fig. 3.** Visual task design. During each 30-min session, participants will complete an image recognition task. Stimuli (faces, houses, and scrambled images) will be presented at the threshold of subjective recognition. Participants' task is to report the category ("F" or "H") of the image presented and their recognition experience ("Yes" or "No").

The stimulus set will include real and scrambled images, where the scrambled images will be created by phase-shuffling a randomly chosen real image from each category to preserve category specific low-level image features [28]. Because scrambled images do not include an object stimulus, they are used as "catch trials" to determine the subjects' baseline tendency to give positive responses to a question about their recognition experience. Each object category will include four unique real images and one scrambled image. Each image will be repeated 10 times (i.e., trials) for each 30-min session. The pre-stimulus interval will vary randomly from trial to trial between 4 and 8 seconds to prevent stimulus timing predictability. The stimuli will be presented in a randomized order to prevent category predictability.

**Primary Outcome Measure:** Blood Oxygen Level Dependent (BOLD) response to visual stimuli (timeframe: baseline to 90 minutes).

**Secondary Outcome Measure:** Perceptual criterion (c) and sensitivity (d') derived from the Signal Detection Theory (SDT) (timeframe: baseline to 90 minutes).

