# **Anticipated Results and Interpretation**

We expect to observe a decrease of both c and d' during sedation, indicating more conservative responses and reduced stimulus differentiation. This would suggest that suppressing the state of consciousness diminishes the quality of conscious content. We also expect to find an overall reduction of average BOLD activity across all examined regions, i.e., in CT (state control), AIC (content gating) and DLPFC (content broadcasting). Furthermore, the change of c (baseline vs. sedation) may be associated with the change of DLPFC's average BOLD activity, and the change of d' may be associated with the change of AIC's average BOLD activity. The change of c × d' may be associated with the change of CT's average BOLD activity. Because the activity of CT supervenes on the activity of DLPFC and AIC, the state (CT) and contents (DLPFC/AIC) are altered together in sedation. If found, the results would suggest a neural mechanism for the linkage between state and contents. We also anticipate that the LIFUP stimulation in DLPFC during sedation will increase c without changing d' and increase the average BOLD activity in the

DLPFC. Stimulation of the AIC will increase d' without changing c, possibly through an enhancement of salience/attentional process offsetting the general inhibitory effect of propofol. Importantly, stimulation of the CT is expected to substantially increase both d' and c, arguably restoring perceptual performance to baseline level. This may be accompanied by an overall increase of average BOLD activity along the entire visual processing pathway.

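### The baseline-to-sedation change in BOLD, c and d' is confounded with session position and, on the plain reading of the stimulus plan, with prior exposure to the same pictures

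*Combined protocol and SAP*

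**What the plan says.** All references are to the combined protocol and SAP.

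- **Order.** Experimental Design: "Three 30-min sessions will be conducted including wakeful baseline, moderate sedation, and the application of LIFUP under moderate sedation". Also: "A 5-min equilibration period between baseline and moderate sedation will be included". At the end, "After sedation+LIFUP session, the infusion will be terminated allowing for spontaneous recovery of consciousness"; no task session after that point is described.
- **Randomisation.** "A random group assignment will be applied in four groups of participants receiving LIFUP with sham control, or in the DLPFC, AIC, or CT, respectively". What is randomised is the LIFUP target or sham. Propofol is given to everyone, at the same target concentration in both sedated sessions.
- **Stimuli.** Experimental Design, Visual task: "Each object category will include four unique real images and one scrambled image. Each image will be repeated 10 times" in each session. Trial order is randomised so that the category cannot be predicted. Contrast is titrated for each participant to 50% recognition; whether this is repeated for later sessions is not stated.
- **Analysis.** Data Analysis and Statistics plans repeated-measures ANOVA with post-hoc comparisons and regressions of SDT metrics on BOLD, under FDR control. It names no term for time, session position or exposure.
- **Interpretation.** Rationale and Hypothesis states the first aim: "we aim to determine how conscious contents are degraded during anesthetic modification of the conscious state". Anticipated Results and Interpretation says of the expected fall in c and d' under sedation: "This would suggest that suppressing the state of consciousness diminishes the quality of conscious content". It also expects lower BOLD, the primary outcome. Both sections expect stimulation of the central thalamus (CT) to bring perceptual performance back to its awake level.

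**The concern.** Every participant is awake in session 1 and sedated in session 2. The state of interest and the position in the visit change together, and nobody does the second session unsedated. A change between the two sessions can reflect propofol, time in the scanner, fatigue, practice with the task or, if the pictures are reused, familiarity with them.

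The direction is not predictable. Fatigue or a weakening response to repeated pictures would look like the expected decline. Learning the pictures would work against it and could hide a real fall in c or d'. False alarms come from only two scrambled pictures, and the false-alarm rate enters both c and d', so a learned response to those two pictures would move both metrics.

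At stake are the first aim, the expected sedation effect on the primary outcome, and the restoration claim. That claim compares session 3 with session 1, two sessions that differ in position and possibly in exposure as well as in treatment.

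**Working it through.** **1. What varies with what.**

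| Session | State | Position | Prior showings of each picture in the main task, if reused |
|---|---|---|---|
| 1 | awake | first | 0 |
| 2 | sedated | second | 10 |
| 3 | sedated + LIFUP or sham | third | 20 |

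The first three columns are the same for all participants in all four groups, apart from the LIFUP target in session 3. State and position coincide exactly in the session 1 versus 2 contrast, so that contrast alone has no information to separate them. In session 3 all groups share position and exposure, so LIFUP versus sham is clean.

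**2. Counts (Visual task).** Images: 2 × (4 + 1) = 10. Trials per session: 10 × 10 = 100, of which 2 × 4 × 10 = 80 show real images and 2 × 1 × 10 = 20 are catch trials. Over three sessions, a reused picture is shown 30 times, plus any titration.

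**3. The plan's own sample size (Power Analysis).** The plan gives d = 0.56, 80% power, α = 0.05 and N = 24. For a paired contrast, two-sided normal approximation:

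n = ((1.960 + 0.842) / 0.56)² = 25.03, rounded up to 26.

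The exact two-sided t calculation gives 28 and the exact one-sided one 22. A two-sample comparison would need 51 per group. The stated 24 is therefore close only to a within-subject calculation, which is the type of contrast at issue.

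**4. Illustration: a pure order shift with no propofol effect.** Assume a shift of d standard deviations of the paired difference. The two-sided 5% paired t test has noncentrality d√n on n − 1 degrees of freedom.

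| Assumed shift d | d√n, n = 25 | called significant | d√n, n = 100 | called significant |
|---|---|---|---|---|
| 0.2 | 1.0 | 16% | 2.0 | 51% |
| 0.3 | 1.5 | 30% | 3.0 | 84% |
| 0.4 | 2.0 | 48% | 4.0 | 98% |

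The n = 25 column is one group. The n = 100 column pools all four, since the contrast is common to them. Neither includes FDR correction. More participants make such a shift easier to detect and no easier to tell from a drug effect.

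**5. Does preprocessing remove it?** High-pass filtering, drift regression and normalisation of each voxel's time course are applied to the run time series. They do not remove a between-session order effect on the task-evoked response, and they do not touch c or d'.

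**6. Precision of a sham-arm drift correction.** Set the SD of a session-to-session change to 1 and treat sessions as exchangeable, so that consecutive changes have covariance −0.5.

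- Variance of the pooled session 1-to-2 change: 1/100 = 0.01.
- Variance of the sham session 2-to-3 change: 1/25 = 0.04.
- Covariance of the two means: −0.5 × 25 / (100 × 25) = −0.005.
- Variance of their difference: 0.01 + 0.04 + 2 × 0.005 = 0.06, six times the uncorrected variance; SE 0.245.
- Power for d = 0.56: Φ(0.56/0.245 − 1.96) ≈ 63%.

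The sham arm can inform the question, but with limited precision.

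**The case against.** The case for the plan has real force on several points.

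- **Reuse of pictures is not stated.** The plan gives a set size per category and repetitions per session. A reader might take it as fact that the same ten pictures return each time. That is the plain reading because only one set is described, but it remains an inference. If sets do differ, the exposure part falls away and the position part stays.
- **Awake-first order is an ordinary limit of a single-visit drug study.** This may well be the practical reason. The plan neither gives it nor lists the limitation, and its interpretation carries no qualification.
- **The order effect is assumed.** The documents give no estimate. The percentages would apply to any fixed-order paired test with such a shift, and FDR correction would lower them. They show sensitivity and are no evidence that a shift exists.
- **Separation is not wholly impossible.** The sham arm's session 2-to-3 change estimates drift at constant sedation, under assumptions. The plan does not propose this check.
- **A uniform shift does not bias the change-on-change regressions.** It goes into the intercept. Only differences between participants in drift could contribute to those associations.
- **Restoration is worded cautiously** in Anticipated Results and Interpretation, but the comparator is still session 1.

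These points narrow the concern. They do not remove the confounding of the baseline-to-sedation contrast.

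**Conclusion.** The point holds in a limited form. The baseline-to-sedation change in BOLD, c and d' is confounded with session position by design. On the plain reading of the stimulus description it is also confounded with 10 prior showings of each picture. A comparison of session 3 with session 1 carries two steps of position and, on the same reading, 20 prior showings. Size and direction are unknown; the 16–48% (n = 25) and 51–98% (n = 100) figures rest on an assumed shift of 0.2 to 0.4 SD and an uncorrected two-sided 5% test.

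Two stronger readings are not supported. One is that the expected sedation effect is an artefact: nothing in the documents shows an order effect, and learning could as easily mask a true effect. The other is that the LIFUP findings are compromised: the randomised session-3 comparison with sham has the same order and exposure in every group. This is an inexpensive improvement that changes what the sedation result can be said to show.

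**What to change.** 1. **Rotate image sets.** Prepare three matched sets, each with four real and one scrambled image per category (24 real and 6 scrambled in all). Use one set per session and rotate the set-to-session assignment across participants within each group. If separate sets are already intended, say so. Real and scrambled images then stay equally repeated. A new scramble for every catch trial beside repeated real images is not advised, because familiarity would itself become a cue in d'. *Cost:* stimulus preparation and programming, titration that must cover all sets, small between-set differences, and only near-exact balance in groups of 25 (8/8/9). This removes picture-specific repetition; time in the scanner and fatigue remain.
2. **Report drift.** Beside the baseline-to-sedation effect, give the sham arm's session 2-to-3 change in BOLD, c and d'. State the assumptions: equal drift per session, no interaction with sedation, and no effect of sham itself. If drift slows with exposure, this change will understate the drift from session 1 to 2. Add an early-versus-late-half comparison within baseline for BOLD (about 40 real-image trials per half). A trend in c and d' by single repetition is not workable, since each repetition has only two catch trials. *Cost:* two descriptive analyses, with the limited precision shown above.
3. **Qualify the interpretation.** In Anticipated Results and Interpretation, describe the baseline-to-sedation result as sedation together with session order. Base causal LIFUP statements, including restoration, on the randomised comparison with sham. *Cost:* wording only.

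An awake control group would address position directly, but needs about 34 more participants for 80% power at d = 0.56 against 100 sedated: Φ(0.56/√(1/100 + 1/34) − 1.96) ≈ 0.80. It is not asked for here.
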